Hypotheses: The effects of infant age of egg introduction and frequency of egg intake will vary by the child outcome of interest (**Hypothesis 1**). We predict a non-linear association between age of egg introduction and the average probability of multiple child outcomes (i.e., stunting, underweight, obesity, high risk of metabolic syndrome, food allergy, and cognitive delay), with the optimal age being a time point that falls between 6-12 months (**Hypothesis 2**). We also predict a non-linear association between frequency of infant egg intake and the average probability of multiple child outcomes, with the optimal frequency being 2-4 times per week (**Hypothesis 3**).

3) Project Design:

Sample/Data. We propose a 2-year study to examine the extent to which two important aspects of infant egg consumption (i.e., age of introduction and frequency of intake) influence physical growth, obesity, cardio-metabolic health, risk of food allergy, and cognition development in mid-childhood and adolescence. Guided by a life course framework (**Figure 1**), we will use existing secondary data from two US longitudinal birth cohorts that tracked mother-child dyads from pregnancy to adolescence: 1) **Project Viva** (1999-present, N=2,128 newborns) that followed children at delivery, 6 months (m), 1 year (y), 2 y, 3 y, 4 y, 5 y, 6 y, 7 y, 8 y, 9 y, 10 y, 11 y, 12-13 y, 14 y, and 15 y of child age,³⁷ and 2) **Infant Feeding Practices Study II** (IFPS II, 2005-2012, N=3,033 newborns) that followed children at neonatal (1 m), 2 m, 3 m, 4 m, 5 m, 6 m, 7 m, 9 m, 10 m, 12 m, and 6 y of child age.^{38,39} The PI has access to both datasets, and has 3 publications on infant nutrition, early childhood diet, growth, and obesity using Project Viva^{40,41} and IFPS II⁴² data since 2014. These two studies have a similar study design and complementary measures of child outcomes, which provide a unique opportunity for comprehensive analysis on the health effects of infant egg consumption and also external replication of findings.

Exposure measures (infant egg consumption). We will focus on age of introduction and frequency of intake as the key exposure measures of infant egg consumption, because evidence

Infant Egg Consumption | Child Health and Cognition | Clinical Guidelines

Figure 1. Conceptual framework on effects of infant egg consumption

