supports their potential influences on child health and development⁴³. We recognize that other aspects of infant egg consumption such as different egg fractions (i.e., white vs yolk⁴⁴) may also influence child outcomes but they were not collected in Project Viva or IFPS II.

Age of egg introduction. At **Project Viva** visits, the age of infant egg introduction was asked at 6-m and 12-m using the same question - “How old was your baby when you first fed him/her eggs”. In the **IFPS II**, mothers reported their infant’s intake of 18 types of foods in the past 7 days through monthly surveys from 2-12 m of infant ages. The question used for infant food intake was - “In the past 7 days, how often was your baby fed each food listed below? Include feedings by everyone who feeds the baby and include snacks and night-time feedings.” “Eggs” were one of the 18 types of foods. Accordingly, we will derive the infant age of egg introduction from IFPS II mothers’ monthly responses to infant egg consumption. Our previous analysis on infant dietary patterns showed that 1.7% and 63.0% of IFPS II infants had been introduced eggs by 6 m and 12 m of age, respectively⁴².

Frequency of egg intake. At the 2-y survey in **Project Viva**, the frequency of infant egg intake in the past month was obtained from the mothers’ response to the question - “Please check the box that best represents how often your child eats each of the foods listed, on average, in the past month”. One of the food items for this question was “Whole eggs”. Response options for the frequency of consuming “Whole eggs” included “never”, “<once/week”, “once/week”, “2–4 times/week”, “nearly daily or daily”, and “≥2 times/day”.

The same question was asked again at surveys at 3 y and 7 y. As mentioned above, mothers in the IFPS II reported their infant's intake of eggs in the past 7 days through the monthly surveys from 2-12 m of infant ages. Infant egg intake was reported as the number of feedings per day or per week. Our analysis on infant dietary patterns showed the mean egg intake among IFPS II infants was 0.01 (SD, 0.10) and 0.27 (SD, 0.37) serving/week at 6 m and 12 m, respectively⁴².

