In addition, we will create an **average probability of multiple child outcomes** to balance across different aspects of child health and development using the methods published by Oken et al.⁵³ for identifying the lowest-risk exposure level when multiple outcomes are considered. Specifically, we will focus on 6 binary child outcomes including stunting, underweight, obesity, high risk of metabolic syndrome (e.g., z score $\geq 95^{\text{th}}$ percentile), food allergy, and cognitive delay (e.g., standardized cognition score < 85 points). We will use estimates from aforementioned logistic models to generate predicted probabilities of each of the 6 adverse outcomes when the independent variable of infant egg consumption (i.e., age of egg introduction or frequency of egg intake) varies across the observed range within our study sample. We will calculate the average probability of the 6 outcomes, assuming these outcomes are equally important. We will identify the lowest-risk infant egg consumption when the corresponding average probability of the 6 adverse outcomes is the lowest.

We will handle missing data with Multiple Imputation.⁵⁴ Specifically, we will first generate 20 replicates of datasets (PROC MI in SAS) with imputed values for missing data on infant egg consumption, child outcomes, and significant covariates, based on a bayesian approach. The 2nd stage is to use standard statistical methods (e.g., Linear Regression) to fit the model of interest to examine the association between infant egg consumption and the specific outcome within each of the 20 imputed datasets. The 3rd stage is to pool the analytic results from all 20 imputed datasets to get the average estimates of the association (PROC MIANALYZE). The PI has experience with Multiple Imputation for large datasets.⁵⁵

All our analyses will be first conducted among boys and girls separately to examine the potential sex differences. A formal interaction test will be conducted by including the interaction term of egg consumption and sex into the regression models. If the interaction term is significant, sex-stratified results will be reported. Otherwise, sex-pooled analytic results will be reported.

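### The plan does not require an imputed age of egg introduction to be later than the infant's last egg-free survey, so infants who drop out at about 9-10 m can be imputed into the 6-8 m category

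*Combined protocol and SAP*

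**What the plan says.** The paragraph on age of egg introduction (Project Design, exposure measures) obtains age differently in the two cohorts.

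- **Project Viva:** "the age of infant egg introduction was asked at 6-m and 12-m using the same question".
- **IFPS II:** age is not asked. Mothers reported on "types of foods in the past 7 days through monthly surveys from 2-12 m of infant ages", and the plan states that "we will derive the infant age of egg introduction from IFPS II" survey responses. The follow-up ages listed under Sample/Data between the neonatal survey and the 6-year survey are "2 m, 3 m, 4 m, 5 m, 6 m, 7 m, 9 m, 10 m, 12 m", so no 8 m or 11 m survey is listed.

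The same paragraph reports that "1.7% and 63.0% of IFPS II infants had been introduced eggs by 6 m and 12 m of age, respectively".

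The only missing-data rule is the multiple imputation paragraph under Data analysis. Twenty datasets are created with PROC MI, containing "imputed values for missing data on infant egg consumption, child outcomes, and significant covariates, based on a bayesian approach". The model of interest is fitted in each and the results are pooled. The plan does not name the level at which egg consumption is imputed, sets no lower limit on an imputed age, and has no rule for an infant followed for only part of the first year.

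**The concern.** A mother who returns egg-free surveys to 9 m and then stops has given a right-censored age (later than 9 m under the plan's derivation), not an unknown one. The exposure paragraph derives one age per infant, and the missing-data paragraph then imputes egg consumption alongside outcomes and covariates before fitting regressions on that exposure. Read together, they most naturally mean that the derived age is imputed. An ordinary PROC MI draw for that variable has no child-specific lower limit and can put this infant at 6-8 m.

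The same gap affects a Project Viva mother who reports no eggs at the 6 m visit and misses the 12 m question.

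What is at stake is the window of Hypothesis 2, which places the optimal age between 6 and 12 m. Aim 1 separates 6-8 m from 9-11 m and looks for thresholds, and the average-probability analysis searches for the lowest-risk age. Moving late or never starters into 6-8 m blurs the comparison on which these rest.

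**Working it through.** **Inputs from the plan.** Cumulative introduction in IFPS II: F(6) = 1.7%, F(12) = 63.0%. These are observed results from a previous analysis and cannot be recomputed here. N = 3,033.

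**Assumed.** The dropout rate (not in the documents) is taken as 10-30% of infants still egg-free at 9 m, all leaving then. The shape of F between 6 and 12 m is also not given and is varied below.

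**1. Normal age curve through the two figures.**
SD = (12 − 6)/(z₀.₆₃ − z₀.₀₁₇) = 6/(0.332 + 2.120) = 2.447 m.
Mean = 12 − 0.332 × 2.447 = 11.19 m.
F(9) = Φ((9 − 11.19)/2.447) = 18.6%.

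**2. Imputed ages that contradict the record (simulation, unbounded normal imputation).** The share of dropouts' imputed ages below 9 m is about 20% at 10% dropout and 22% at 30%. It exceeds 18.6% because the imputation model is fitted to responders, from whom late starters have been removed. Only about 2-3% of these imputed ages fall below 6 m.

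**3. Contamination of the group labelled under 9 m.**
- 30% dropout: dropouts are 0.30 × (1 − 0.186) = 24.4% of the cohort. Wrongly placed: 24.4% × 0.22 = 5.4%. Share of the group: 5.4/(18.6 + 5.4) = 22.5%, or about 23%.
- 10% dropout: 0.10 × 0.814 = 8.1%. Wrongly placed: 8.1% × 0.195 = 1.6%. Share: 1.6/(18.6 + 1.6) = 8%.

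**4. Other curve shapes.** If a draw ignores the returned surveys, the share contradicting an egg-free record to month t is F(t). At 9 m, linear interpolation gives 0.017 + 0.613 × 3/6 = 32%. A late-rising curve gives 0.017 + 0.613 × (3/6)² = 17%, and an early-rising one 0.017 + 0.613 × √(3/6) = 45%.

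| Last egg-free survey | Linear | Range over shapes |
|---|---|---|
| 6 m | 1.7% | 1.7% |
| 7 m | 12% | 3-27% |
| 9 m | 32% | 17-45% |
| 10 m | 43% | 29-52% |

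For a record egg-free to 9 m, 6-8 m receives F(9) − F(6), about 31% of draws (15-43%). All categories below 6 m together receive 1.7%. In the linear case with 10-30% dropout at 9 m, 3,033 × 0.10 × 0.676 × 0.324 = 66 to three times that, 199, infants per imputed dataset would be misplaced (2.2-6.6%).

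**5. Effect on estimates (simulation).**
- *True step at 9 m, outcome in the imputation model:* the 6-8 m versus 9-11 m contrast shrinks by about 5-6% at 10% dropout and 15-16% at 30%.
- *Same step, outcome left out:* it shrinks by 8-23%.
- *Linear truth:* the contrast is essentially unchanged, and so is the slope (0.0405 true, 0.0402-0.0416 imputed).

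**6. The opposite default.** Coding early dropouts as never introduced is also wrong: (63.0 − 1.7)/(100 − 1.7) = 62% of infants egg-free at 6 m start by 12 m.

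**The case against.** **The plan may already intend the right thing.** A reader might infer that the plan discards the egg-free surveys. It does not say so. The exposure paragraph also uses the term egg consumption for the monthly responses, and imputing those before deriving age would be compatible with the text. This stands: the point is an unspecified level and a missing constraint, with a natural reading that leads to error, not a declared error.

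**Early introduction is barely touched.** A reader might infer that all early categories are corrupted. With 1.7% introduced by 6 m, those below 6 m are not materially affected. The problem sits in 6-8 m and arises mainly from dropout at about 9-10 m. This stands.

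**Such ages are not strictly impossible.** Each survey covers 7 days and no 8 m or 11 m survey is listed. The plan's mean intake at 12 m of 0.27 serving/week, divided by 63.0% introduced, is about 0.43 per introduced infant. Under an assumed Poisson pattern, exp(−0.43) = 65% of introduced infants would report no egg in a given week. So an egg-free survey bounds the derived age, not true first exposure. This stands as a reason for a sensitivity analysis. It does not excuse treating partial responders differently from complete responders, whose age is derived from the same records.

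**The size rests on assumed dropout.** This also stands. Spreading 30% dropout evenly over last egg-free surveys at 3-10 m lowers the contaminated share of the under-9 m group to 8%, with 7% of imputed ages contradicting the record.

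**The normal curve assigns ages beyond 12 m, which the IFPS II infant surveys do not observe.** True, so no weight is put on imputed versus true mean ages. The calculation in step 4 needs no ages beyond 12 m and gives 17-45% at 9 m.

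**Conclusion.** The concern holds as a gap in the specification of the imputation, worth correcting before analysis. If the derived age is imputed without a bound, and 10-30% of infants egg-free at 9 m drop out then, about 20-22% of their imputed ages contradict the record under the normal curve (17-45% for unrestricted draws under other shapes). Such infants form 8-23% of the group labelled under 9 m. The consequence is moderate: about 5-16% attenuation of a true step at 9 m in the 6-8 m versus 9-11 m contrast, and essentially none for linear associations. The effect on the fractional polynomial curve and on the selected lowest-risk age was not computed. The dropout rate, its timing and the shape of the introduction curve are all assumptions. The point concerns children lost before 12 m, not those observed egg-free to 12 m.

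**What to change.** State the level of imputation and add a rule for partly observed ages.

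- **IFPS II, preferred:** impute the yes/no egg status of each missed survey in time order given all earlier statuses (PROC MI, FCS logistic), carry a positive status forward, and derive age of introduction afterwards.
- **IFPS II, where early statuses are too sparse for logistic models:** impute the derived age bounded below by the last egg-free survey, with not introduced by 12 m as a possible result.
- **Project Viva:** for infants egg-free at the 6 m visit whose 12 m answer is missing, restrict the imputed age to above 6 m.
- **Both cohorts:** do not code early dropouts as never introduced.
- **Sensitivity analysis:** relax the IFPS II bound, because of the 7-day window and the months with no listed survey.
- **Reporting:** tabulate dropout by last egg-free survey, so that the size of the problem can be seen.

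The cost is SAP wording and additional programming, with no new data. The downside is more imputation variables in IFPS II and possibly unstable logistic models in the early months, where few infants have had egg.

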Cognition development. In Project Viva, the child's cognition development, including intelligence, visual-motor, and memory-learning, was measured at 3 y and 7 y of age⁵⁰. For the intelligence domain, trained research staff administered the Peabody Picture Vocabulary Test-3rd edition (PPVT-III, a test of receptive language) at 3 y of age, and the Kaufman Brief Intelligence Test-2nd edition (KBIT-II, verbal and non-verbal intelligence) at 7 y of age. For the visual-motor domain, research staff administered the Wide Range Assessment of Visual Motor Abilities (WRAVMA) at the 3-y visit. WRAVMA includes the fine motor (pegboard), visual spatial (matching), and visual motor (drawing) subtests. Subtest scores were combined to yield the total WRAVMA score. At the 7-y visit, staff administered the WRAVMA visual motor (drawing) subtest only. For the memory-learning domain, staff administered the design memory and picture memory subsets of Wide Range Assessment of Memory and Learning (WRAML) at the 7-y visit. These two subset scores were combined to yield the total WRAML score.

Effect modifier. We are interested in effect modification by child sex (Boys vs Girls).

Confounders. Potential confounders include family income; health history of family members; parental education attainment, employment, and preconception BMI; and maternal intelligence, age, race/ethnicity, marital status, parity, pregnancy complications, prenatal vitamins, smoking, and delivery method; early mode of infant feeding including breastfeeding duration and exclusivity. We will also adjust for child actual age at assessments.

Data analysis. All our analyses will be first conducted among boys and girls separately to examine the potential sex differences (if significant, sex-stratified results will be reported).

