Statistical Power. We expect sufficient statistical power for our hypothesis-driven data analyses for both Aims, because 1) the 2 cohorts had relatively large sample sizes (N=2,128 for Project Viva and N=3,033 for IFPS II), which are sufficient to detect a small odds ratio (1.46 for Project Viva, 1.38 for IFPS II with type 1 error being 0.05 and power being 0.8) of binary child outcomes (e.g., food allergy) between infants with different egg consumption (e.g., egg introduced at ≥ 12 m vs 6-8 m) or a small effect (effect size=0.054 for Project Viva, 0.051 for IFPS II) of infant egg consumption on continuous outcomes (e.g., intelligence score); 2) most child outcomes were measured repeatedly; 3) infant egg consumption varied largely within cohorts.

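### A significance test on the egg-by-sex term decides whether pooled or sex-specific results are reported, and the plan does not say which population feeds the six-outcome average

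*Combined protocol and SAP*

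**What the plan says.** Child sex is the only effect modifier named (section 3, Project Design, Effect modifier). The Data analysis text opens with "All our analyses will be first conducted among boys and girls separately", and its closing paragraph repeats this. That paragraph then adds: "A formal interaction test will be conducted by including the interaction term of egg consumption and sex into the regression models". The result of the test determines the output: "If the interaction term is significant, sex-stratified results will be reported. Otherwise, sex-pooled analytic results will be reported". The opening lines of Data analysis carry the same condition in brackets.

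Models are fitted by outcome and by exposure (Aims 1 and 2), so one interaction test per outcome and exposure is the natural reading, though it is not spelled out. No significance level, multiplicity adjustment or power is given for this test. The only type 1 error in the document is in Statistical Power, "with type 1 error being 0.05 and power being 0.8", and it concerns the main association.

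The average over stunting, underweight, obesity, high metabolic risk, food allergy and cognitive delay is built from the logistic models already described: "We will calculate the average probability of the 6 outcomes, assuming these outcomes are equally important". The plan does not say whether those models are pooled or sex-specific. The average identifies the lowest-risk age and frequency, which are the subject of Hypotheses 2 and 3.

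**The concern.** The rule is either/or. A significant interaction removes the pooled estimate from the report; a non-significant one removes the boys' and girls' estimates, although these will already have been computed. What the reader sees for each outcome therefore depends on a p-value. Two kinds of error follow. With many tests and no correction, some outcomes will switch to stratified reporting by chance. With a weak test, a real sex difference will often be missed and only the pooled figure shown.

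The average raises a separate question. If some of its components show an interaction and others do not, the plan gives no instruction on which estimates enter. An average that combined sex-specific probabilities for some outcomes with pooled probabilities for others would describe no single group of children, and neither would the lowest-risk value read from it.

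**Working it through.** **Inputs from the documents.** Sample sizes: "N=2,128 for Project Viva and N=3,033 for IFPS II". Detectable odds ratios: "1.46 for Project Viva, 1.38 for IFPS II". Type 1 error 0.05 and power 0.80, for the main association. Six outcomes in the average; two exposures.

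**Assumptions.** The interaction test is done once per outcome and exposure at two-sided 0.05. For power, boys and girls are equal in number and precision.

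**1. The plan's own figures.** The reference risk and group split are not stated. Assume a risk of 10%, a 1:1 split of the whole cohort and two-sided 0.05. The detectable odds ratio then solves (p1 − p0) / √[(p0(1 − p0) + p1(1 − p1)) / (N/2)] = 1.960 + 0.842 = 2.80.
- Project Viva: an odds ratio of 1.458 gives p1 = 0.162/1.162 = 0.1394, and 0.0394 / √[(0.0900 + 0.1200)/1,064] = 0.0394/0.01405 = 2.80.
- IFPS II: an odds ratio of 1.376 gives p1 = 0.1326, and 0.0326 / √[(0.0900 + 0.1150)/1,516.5] = 0.0326/0.01163 = 2.80.

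These round to the stated 1.46 and 1.38. Other pairs fit about as well (for example 30% exposed with a risk near 12%). Step 4 does not depend on the pair; it uses only the statement that these odds ratios have 80% power.

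**2. Number of tests.** Project Viva can supply all six components. Cardio-metabolic measures and cognition tests are described for Project Viva only, so IFPS II can supply at most four: stunting, underweight, obesity and food allergy.

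**3. Chance of at least one false switch, no true interaction.** For m independent tests this is 1 − 0.95^m.

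| Setting | m | Chance |
|---|---|---|
| Project Viva, one exposure | 6 | 1 − 0.7351 = 26.5% |
| Project Viva, both exposures | 12 | 1 − 0.5404 = 46.0% |
| IFPS II, one exposure | 4 | 1 − 0.8145 = 18.5% |

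The outcomes are measured in the same children, and some share ingredients (obesity and underweight are both BMI cut-offs). Simulating six equally correlated normal statistics gives 20.7% at correlation 0.5 and 13.8% at 0.8. The independent figures are therefore upper values.

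**4. Power of the interaction test.** Let SE be the standard error of the pooled log odds ratio. Each sex alone has standard error √2 × SE, so the difference between the sexes has √(2 + 2) × SE = 2 × SE. An effect with 80% power in the pooled analysis lies 2.80 SE from zero. The same quantity as a ratio of odds ratios lies 2.80/2 = 1.40 standard errors from zero. Power = Φ(1.401 − 1.960) + Φ(−1.401 − 1.960) = 0.288, about 29%. Reaching 80% power needs twice the log effect: 1.46² = 2.13 in Project Viva and 1.38² = 1.90 in IFPS II.

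**5. How often the six tests would disagree.** Suppose all six outcomes had the same true interaction, each tested independently with power 0.288. The tests would be neither all significant nor all non-significant with probability 1 − 0.288^6 − 0.712^6 = 0.87. Disagreement among the components is thus a likely case, and the plan gives no rule for the average when it occurs.

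**6. Would correction alone cure it?** Bonferroni over six outcomes (0.05/6 = 0.0083) lowers the chance of a false switch to 1 − (1 − 0.0083)^6 = 4.9%, but power in step 4 falls to Φ(1.401 − 2.638) = 11%. It trades one error for the other.

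**The case against.** The best defence is that this is orderly planning. One modifier is named in advance, a formal test is specified and the consequence is written down. That stands: a reader might infer an after-the-fact choice of subgroup, and the documents do not support that. The rule is prespecified, but its output still depends on the data.

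A reader might also infer that the plan sets 0.05 for the interaction test. It does not; 0.05 appears only in Statistical Power, and every false-switch figure above is conditional on it.

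The strongest tempting reading is that the plan will build its average from a mixture of pooled and sex-specific models. The text does not say so. The rule governs what is reported, and nothing says that the test selects the inputs to the average. Since all analyses are also to be run by sex, an all-boys and an all-girls average could be produced under the plan as it stands. What remains is silence: a mixed average is possible, not planned.

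One could also multiply six outcomes by two exposures and two cohorts and quote 1 − 0.95^24 = 71%. The documents do not support 24 tests, because two of the six components are not described for IFPS II.

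Finally, the plan nowhere states that a non-significant test will be taken as proof of no sex difference. The criticism is that the estimates a reader would need to judge this go unreported.

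**Conclusion.** The concern holds as a moderate, easily mended weakness. The reporting rule is prespecified but data-dependent, and the test that drives it has no stated level, multiplicity control or power. At an assumed 0.05 per outcome with no true interaction, the chance of at least one false switch in Project Viva is between about 14% (correlation 0.8) and 26% (independence) per exposure, and at most about 46% over both exposures; in IFPS II it is at most about 19% per exposure. The 29% power figure rests on equal numbers and precision by sex and on taking the plan's detectable odds ratios at face value. With power that low, reporting pooled results alone after a non-significant test can conceal a real difference. The population behind the six-outcome average needs to be stated, because Hypotheses 2 and 3 rest on it.

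**What to change.** Replace the either/or rule. For every outcome and both exposures, report the pooled estimate, the boys' and girls' estimates, and the interaction estimate with its 95% CI, whatever the test shows. If an interaction p-value is still used in interpretation, state its level and how multiplicity is handled.

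For the six-outcome average and the lowest-risk value, state that all components come from models fitted in the same population: all pooled as the main result, then all boys and all girls as secondary results. The chance of a mixed average is then zero, whatever the interaction tests show.

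The sex-specific fits are already planned, so the cost is a few sentences in the analysis plan and longer supplementary tables.

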For **Aim 1 (infant age of egg introduction)**, we will first classify the infants based on their age of egg introduction: never, <2 m, 2-3 m, 4-5 m, 6-8 m, 9-11 m, and 12 m. Then we will compare their physical growth, obesity, cardio-metabolic risk profile, risk of food allergy, and cognition test scores in mid-childhood and adolescence using Chi-square tests (categorical outcomes) or ANOVA tests (continuous outcomes). We will fit multivariable linear (continuous outcomes) or logistic (binary outcomes) regression models with fractional polynomial functions of infant age of egg introduction, adjusted for significant confounders. Both linear (e.g., earlier introduction, high probability of the outcome) and non-linear (e.g., threshold effect) associations will be tested. The non-linear trend will be examined through visualization of scatter plots and statistical tests of polynomial term of infant age of egg introduction in the regression models. If the polynomial terms of age are not significant, we will drop it and consider the association to be linear.

Then, we will fit a mixed effect model (SAS PROC MIXED) for continuous outcomes (height z-score and BMI z-score) and a generalized linear mixed effect model (SAS PROC GLIMMIX) for binary outcomes (obesity and diagnosis of food allergy) that were measured repeatedly across multiple age points. The mixed effect model will include random intercepts, random slopes for age effects, and autoregressive variance-covariance matrix across different time points. Independent variables in the model will include infant age of egg introduction, outcome age point (mid-childhood and adolescence), the 2-way interaction term (infant age of

egg introduction × outcome age point), and significant covariates. The 2-way interaction term quantifies the extent to which infant age of egg introduction can affect the specific outcome. The PI has experience with using mixed effect models for examine child growth measures and multiple publications in this area.^{51,52}

For **Aim 2 (frequency of infant egg intake)**, we will first classify the infants based on their frequency of egg intake: never, <once/week, once/week, 2–4 times/week, nearly daily or daily, and ≥ 2 times/day. Then, we will use similar analytic methods mentioned above for Aim 1 to compare their health and developmental outcomes.

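### The two detectable effect sizes for continuous outcomes (0.054 and 0.051) cannot both come from one standardized test: the cohort sizes require a ratio of 1.19, and the stated ratio is 1.06

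*Combined protocol and SAP*

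**What the plan says.** Section 3) Project Design, Statistical Power, makes one statement for both cohorts. Its first reason for expecting adequate power is "relatively large sample sizes (N=2,128 for Project Viva and N=3,033 for IFPS II"). These sizes are said to be enough to detect odds ratios of 1.46 and 1.38, with the settings given as "1.38 for IFPS II with type 1 error being 0.05 and power being 0.8", or, for continuous outcomes, "a small effect (effect size=0.054 for Project Viva, 0.051 for IFPS II) of infant egg consumption on continuous outcomes (e.g., intelligence score").

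Repeated measurement of outcomes and wide variation in egg intake follow as separate reasons 2) and 3).

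The paragraph does not name the effect-size metric, the test or its degrees of freedom, or the sidedness. It gives one N per cohort and no cohort-specific alpha or power. The Data analysis text for Aim 1 sets out its methods without distinguishing the cohorts: "We will fit multivariable linear (continuous outcomes) or logistic (binary outcomes) regression models with fractional polynomial functions of infant age of egg introduction", alongside ANOVA across introduction-age groups and mixed models for repeated outcomes.

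**The concern.** The two figures are presented as consequences of the two sample sizes. IFPS II is about 43% larger than Project Viva (3,033/2,128 = 1.43), so its detectable effect should be clearly smaller. The printed values are almost equal.

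N is fixed in this secondary analysis, so the paragraph's job is to tell readers how small an association each cohort could find. If the two figures rest on different bases, readers cannot use them together for that purpose. One cohort's sensitivity may be overstated, the other's understated, or both overstated.

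**Working it through.** **Inputs**
- N = 2,128 and 3,033, effect sizes 0.054 and 0.051, odds ratios 1.46 and 1.38: Statistical Power paragraph.
- Alpha 0.05 and power 0.80: same sentence, but printed in the odds-ratio clause. Applying them to the continuous clause is an assumption. Step 1 needs only that both cohorts share the same values.
- Metric, df and sidedness: not stated, so varied below.

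**Step 1. Scaling.** For a correlation r or Cohen's f, the detectable value is k/sqrt(N), where k depends on alpha, power, df and sidedness but (at these sizes) not on N.
- Required ratio: sqrt(3033/2128) = 1.194.
- Stated ratio: 0.054/0.051 = 1.059.
- Rounding range: 0.0535/0.0515 = 1.039 to 0.0545/0.0505 = 1.079.

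Exact noncentral-F calculations give 1.194 for every df from 1 to 6. Adding 10 to 30 covariates changes nothing at this precision. On an f-squared scale the required ratio is 1.43, further from the stated one.

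**Step 2. Reproducing each figure alone (1 df).** The multiplier implied by a stated figure is effect size × sqrt(N).
- Project Viva: 0.054 × sqrt(2128) = 2.491 (2.47 to 2.51 with rounding).
- IFPS II: 0.051 × sqrt(3033) = 2.809 (2.78 to 2.84 with rounding).
- Required, z(alpha) + z(power): one-sided 1.645 + 0.842 = 2.486 (from unrounded values); two-sided 1.960 + 0.842 = 2.802.

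Each figure reproduces to three decimals, but under opposite sidedness.

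**Step 3. Both cohorts on one basis (1-df r or f).** Power at the stated value is Phi(effect size × sqrt(N) − z(alpha)).

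| Basis | Project Viva, 80% value | Power at 0.054 | IFPS II, 80% value | Power at 0.051 |
|---|---|---|---|---|
| Two-sided | 0.061 | Phi(2.491 − 1.960) = 70% (69 to 71% with rounding) | 0.051 | Phi(2.809 − 1.960) = 80% |
| One-sided | 0.054 | Phi(2.491 − 1.645) = 80% | 0.045 | Phi(2.809 − 1.645) = 88% (87 to 88% with rounding) |

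Two-sided, 80% power at 0.054 would need N of about (2.802/0.054)² = 2,692. The change from 0.054 to 0.061 moves the variance explained, f²/(1 + f²), from 0.29% to 0.37%.

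**Step 4. Other metrics and df.** An F test on 2 to 6 df gives 0.067 to 0.080 for Project Viva and 0.056 to 0.067 for IFPS II. Cohen's d with an assumed 1:1 split gives 0.121 and 0.102 two-sided, or 0.108 and 0.090 one-sided. Under all of these, both stated figures are too small.

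**Step 5. Cross-check on the odds ratios.** ln 1.46/ln 1.38 = 1.175. The rounding range, ln 1.455/ln 1.385 = 1.151 to ln 1.465/ln 1.375 = 1.199, contains 1.194, so this pair scales as the Ns require. It does not settle the sidedness, because no baseline risk is stated. With a 1:1 split, an assumed 10% risk gives 1.458 and 1.376 two-sided. One-sided, assumed risks of 7% (1.477 and 1.392) and 8% (1.446 and 1.367) bracket the same pair.

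**The case against.** The strongest reply is that the cohorts need not have been treated alike. The Sample/Data text says "These two studies have a similar study design and complementary measures of child outcomes", and complementary measures are not identical ones. Project Viva measured growth at 7, 12-13 and 14-15 years, whereas IFPS II has only the 6-year follow-up after infancy, and the Aim 1 analysis includes mixed models for repeated outcomes. Averaging m correlated measures multiplies the detectable effect by sqrt[(1 + (m − 1) × rho)/m]. Taking Project Viva from 0.0607 down to 0.054, two-sided, needs rho of about 0.58 with m = 2, or 0.69 with m = 3. IFPS II with one measure stays at 0.051, and both printed figures are then reproduced.

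This shows that unreported inputs are possible. It does not rescue the paragraph. No such correlation is given, and the effect sizes are tied to sample size in reason 1) while repeated measurement is claimed separately as reason 2). An unstandardized slope could also produce the pair, if the ratio of outcome SD to exposure SD in Project Viva were 1.059/1.194 = 0.89 of that in IFPS II, but no such inputs are given either.

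Two parts of the reply stand. Carrying alpha and power over to the continuous clause is an assumption. And the replacement values of 0.061/0.051 or 0.054/0.045 hold only for a 1-df r or f; the planned ANOVA over several age groups and the polynomial terms use more df.

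**Conclusion.** The pair is inconsistent as stated. No single standardized effect size, tested the same way at the same alpha and power with the stated Ns, yields 0.054 and 0.051. That conclusion does not depend on metric, df or sidedness, only on the cohorts sharing them.

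A reader might infer more than the documents support:
- **That the Project Viva figure is the wrong one, with true power 70%.** This follows only for a two-sided 1-df r or f. One-sided, Project Viva is right and IFPS II is conservative. The two-sided odds-ratio match at a round 10% risk is a hint, not proof.
- **That sidedness alone decides which figure is off.** Metric and df are also unstated, and on 2 to 6 df both figures are too small.
- **That the paragraph claims an intelligence test in IFPS II.** The documents describe cognitive testing for Project Viva only ("cognition development, including intelligence, visual-motor, and memory-learning, was measured at 3 y and 7 y of age"), but the intelligence score is given merely as an example.
- **That the study is underpowered.** Under a 1-df r or f the detectable effect lies between 0.045 and 0.061, and it stays small on more df (at most 0.080).

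Severity is minor: a sensitivity statement needs correcting, and no planned analysis depends on it.

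**What to change.** Recompute both figures on one basis and restate the pair, naming the effect-size metric, the test and its df, the sidedness, alpha and power. For a 1-df r or Cohen's f at alpha 0.05 and power 0.8, the pair would read 0.061 and 0.051 if two-sided, or 0.054 and 0.045 if one-sided. For a multi-df test, give the values for that df. If cohort-specific settings were used, such as repeated measures or an unstandardized slope, keep the figures and report the inputs behind them (number of measures and assumed correlation, or the SDs of outcome and exposure).

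The cost is one sentence. Depending on the basis chosen, the Project Viva figure becomes slightly less favourable, the IFPS II figure slightly more favourable, or both less favourable. Sample, design and analysis are unchanged.
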